DTG: Neural tube defects	
In a birth surveillance study conducted in Botswana (the Tsepamo study), preliminary results showed that in babies born to women who were taking DTG when they became pregnant there was an increased risk of neural tube defects compared with the background rate. Later data from the study has shown a numerically higher rate of neural tube defects with exposure to DTG (0.19%) compared to non-DTG-containing antiretroviral regimens at the time of conception (0.11%), however, the difference was not statistically significant. A causal relationship of these events to the use of dolutegravir has not been established. No increased risk of these defects was reported in babies born to mothers who started dolutegravir containing regimen later in pregnancy. Dolutegravir was tested in a complete package of reproductive toxicology studies, including embryofetal development studies. No adverse development outcomes, including neural tube defects, were identified. In reproductive toxicity studies in animals, DTG was shown to cross the placenta. Data analysed to date from other sources including the Antiretroviral Pregnancy
	
 1. A female subject is eligible to participate if she is not pregnant, not lactating, and, if she is a female of reproductive potential, agrees to follow one of the options listed in the Modified List of Highly Effective Methods for Avoiding Pregnancy in Females of Reproductive Potential (FRP) (see Appendix 9, Section 12.9.1) from 30 days prior to the first dose of study medication and until the last dose of study medication and completion of the Follow-up visit. 2. Women who are breastfeeding or plan to become pregnant or breastfeed during the study are excluded; 3. Women who become pregnant, or who desire to be pregnant while in the study will have study treatment discontinued and will be withdrawn from the study. 4. Females of reproductive potential are reminded re: pregnancy avoidance and adherence to contraception requirements at every study visit. 
Pregnancy status is monitored every 4 weeks throughout the study.

CONFIDENTIAL

Potential Risk of Clinical Significance	Data/Rationale for Risk	Mitigation Strategy
Investigational Product (IP) [DTG/RPV FDC] Refer to individual IBs for DTG and RPV and the Juluca SmPC for additional information		
	Registry, clinical trials, and post-marketing data are insufficient to address the risk of neural tube defects with DTG.	

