5 ELIGIBILITY CRITERIA

5.1 Inclusion criteria

Patient volunteers who meet all of the following criteria are eligible for this trial:

1. Is male or female aged 18 years or over.
2. Has documented HIV-1 infection.
3. Is capable of giving informed consent.
4. Is willing to comply with the protocol requirements.
5. Virologically suppressed (plasma HIV-RNA <50 copies/mL) and on a stable regimen for >24 weeks.
6. Subjects are required to have a history of the K103N mutation (acquired or selected). Subjects who at any time have had the mutations 100I, 101E/P, 106A/M, 138K/G/Q, 181C/I/V, 188L, 190A/S/E/Q, 230L mutations are to be excluded. Other NNRTI region variants can be included. All PI and NRTI mutations are acceptable. Study sites may ask the coordinating centre for advice as required.
7. Subjects must have never failed INSTI (2 x VL >200 >2 weeks apart) but current regimen can include INSTI.
8. A female, may be eligible to enter and participate in the study if she:

is of non-child-bearing potential defined as post-menopausal (12 months of spontaneous amenorrhea without an alternative medical cause and \geq 45 years of age). A high follicle stimulating hormone (FSH) level consistent with postmenopausal status may be used to confirm a post-menopausal state in women who are not using hormonal contraception) or hormonal replacement therapy at the discretion of the PI. However, in the absence of 12 months of amenorrhea, a single FSH measurement alone is insufficient.

OR is physically incapable of becoming pregnant with documented tubal ligation, hysterectomy or bilateral oophorectomy or,

OR is of child-bearing potential with a negative pregnancy test at Screening (& baseline visit) and agrees to use one of the following methods of contraception to avoid pregnancy:

- True abstinence from penile-vaginal intercourse from 2 weeks prior to administration of IP, throughout the study, and for at least 2 weeks after discontinuation of all study medications (When this is in line with the preferred and usual lifestyle of the subject.) (Periodic abstinence (e.g., calendar, ovulation, symptothermal, post-ovulation methods), and

CONFIDENTIAL

- withdrawal are not acceptable methods of contraception];
- Any intrauterine device (IUD) with published data showing that the expected failure rate is <1% per year (not all IUDs meet this criterion, see Appendix 3 for an example listing of approved IUDs);

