 - Male partner sterilisation confirmed prior to the female subject's entry into the study, and this male is the sole partner for that subject;
 - Approved hormonal contraception (see appendix 4 for a listing of examples of approved hormonal contraception);
 - Any other method with published data showing that the expected failure rate is <1% per year;
 - Any contraceptive method must be used consistently and for at least 2 weeks after discontinuation of IP.
9. If a heterosexually active male, he is using effective birth control methods and is willing to continue practising these birth control methods during the trial and until follow-up visit.
10. Subjects currently receiving DTG or RPV, but not both, can be included.

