6.4 Screening

Written informed consent must be obtained from the subject prior to performing any study related evaluations or procedures.

Subjects will be provided with written information about the study in the form of a Participant Information Sheet (PIS) and will be allowed adequate time for questions and to consider the study before agreeing to participate. It will be the responsibility of the investigator or co-investigator to obtain written informed consent prior to undertaking any procedures detailed in the protocol. This responsibility may be delegated to other suitably trained personnel if allowed according to country-specific regulations and approved by the local ethics committee.

The investigator or designee must provide adequate explanation of the aims, methods, objectives, and potential hazards of the study. It must also be explained to the subject that they are free to refuse or withdraw from the study for any reason without detriment to their future care or treatment.

The following evaluations must be performed within 28 days prior to study randomisation:

- Assessment of subject eligibility according to the inclusion and exclusion criteria
- Demographics
- Medical and social history (past and current), including HIV-associated conditions (see Appendix 1)
- Full antiretroviral history (including resistance history i.e. record all resistance history by major mutations in NRTI, NNRTI, PI and II regions).
- Review of non-antiretroviral medication (any medication taken within the last 30 days)
- Concomitant medication check
- Physical examination including height and weight
- Vital signs (pulse, blood pressure): after 10 minutes resting
- Urinalysis (see Appendix 1) and pregnancy test for WOCBP (β -HCG).
- Laboratory evaluations (non-fasting): haematology and biochemistry (Appendix 1)
- Total cholesterol and lipids (HDL, LDL and triglycerides)
- HIV RNA viral load

CONFIDENTIAL

- HBV antigen test (including HbsAG, anti-HBc and HBsAb , if done as per standard practice) and HCV antibodies test (if test positive for HCV antibodies, test for HCV RNA, if positive and chronic for either HBV or HCV, add AST test to the biochemistry panel at screening visit. Hep B surface antibodies post vaccination levels to be included in assessment, if this is part of local practice)
- ECG
- CD4 & CD8 count / % and ratio

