7.10 Trial restrictions

Please refer to inclusion & exclusion criteria listed in sections 5.1 & 5.2.

CONFIDENTIAL

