13.4 Protocol Compliance

Prospective, planned deviations or waivers to the protocol are not allowed under the UK & EU regulations on Clinical Trials and must not be used e.g. it is not acceptable to enrol a subject if they do not meet the eligibility criteria or restrictions specified in the trial protocol.

Accidental protocol deviations can happen at any time. They must be adequately documented on the relevant forms and reported to the Chief Investigator and Sponsor immediately.

Deviations from the protocol which are found to frequently recur are not acceptable, will require immediate action and could be classified as a serious breach.

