Appendix 1: Assessment table

Both treatment arms to complete all visits.	SCREENING	BASELINE (within 28 days of screening)	WEEK 4 (+/- 7 days)	WEEK 12 (+/- 7 days)	WEEK 24 (+/- 7 days)	WEEK 48 (+/- 7 days)	WEEK 52 (+/- 7 days)	WEEK 60 ¹ (+/- 7 Days)	WEEK 72 (+/- 7 days)	WEEK 96 (+/- 7 days)	30 Day FU (+/- 7 days) (by phone)	Early termination visit
Eligibility Criteria Assessment	X											
Informed Consent	X											
Demographic Data	X											
Medical and Social History Including 
 • Recreational drug use • Smoking history • Alcohol intake • Concomitant diseases • Past & present medical history, including HIV- associated conditions • Antiretroviral history (including resistance history i.e. record all resistance history by major mutations in NRTI, NNRTI, PI and II regions) 	X											
Alcohol intake, smoking habit and recreational drug use		X	X	X						X		X
Physical Examination (Including Height)	X											
Weight	X	X	X	X	X	X	X	X	X	X		X
Symptom Directed Physical Exam		X	X	X								
Vital Signs Including: 
 • Pulse • Blood pressure (after 10 minutes resting) 	X	X	X	X			X	X	X	X		X

¹ Week 60 visit is an optional visit at week 60 may be performed for subjects who are on the control arm (3 months after therapeutic modification) as required per national guidelines.

CONFIDENTIAL

	SCREENING	BASELINE (within 28 days of screening)	WEEK 4 (+/- 7 days)	WEEK 12 (+/- 7 days)	WEEK 24 (+/- 7 days)	WEEK 48 (+/- 7 days)	WEEK 52 (+/- 7 days)	WEEK 60 ¹ (+/- 7 Days)	WEEK 72 (+/- 7 days)	WEEK 96 (+/- 7 days)	30 Day FU (+/- 7 days) (by phone)	Early termination visit
Both treatment arms to complete all visits.												
Urine pregnancy test for women of child bearing potential (WOCBP) (β-HCG) only. Investigators to remind females of reproductive potential of the need to avoid pregnancy while in study and adherence to the study's contraception requirements. As a reminder, females of reproductive potential who changed their minds and desire to be pregnant should also be withdrawn from the study.	X	X (Predose)	X	X	X	X	X	X	X	X	X	X
PREGNANCY TESTS and FOLLOW-UP TELEPHONE CALLS TO BE PERFORMED EVERY 4 WEEKS												
Pregnancy Test : Follow-up calls should be made to WOCBP												

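### Inclusion criterion 8 does not carry Table 1.0's contraception window: no lead-in for IUD, hormonal or other low-failure methods, and a minimum tail of 2 weeks instead of up to the Follow-up visit

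*Protocol*

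**What the plan says.** Protocol 1.1, Table 1.0, gives the mitigation for neural tube defects with dolutegravir (DTG). It is worded as a condition of eligibility: the woman agrees to a method from a list of highly effective ones "from 30 days prior to the first dose of study medication and until the last dose of study medication". The sentence goes on to require completion of the Follow-up visit. For the list it cites an Appendix 9.

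Protocol 5.1 opens with "Patient volunteers who meet all of the following criteria are eligible for this trial". For women of child-bearing potential, inclusion 8 asks for a negative pregnancy test at screening and baseline and agreement to one of several methods. Only abstinence has a numeric lead-in (2 weeks). Partner sterilisation must be confirmed before she enters the study. The IUD, hormonal and any-other-method bullets give no start date. The tail for all methods is: "Any contraceptive method must be used consistently and for at least 2 weeks after discontinuation of IP". Exclusion 28 in Protocol 5.2 asks for willingness to use a highly effective method and states no window. Appendix 3, the method list, states none either.

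Sites are directed to 5.1 and 5.2. Protocol 6.4 lists "Assessment of subject eligibility according to the inclusion and exclusion criteria" among the screening tasks, and 7.10 refers for trial restrictions to the inclusion and "exclusion criteria listed in sections 5.1" and 5.2. Protocol 13.4 adds that "it is not acceptable to enrol a subject if they do not meet the eligibility criteria or restrictions specified in the trial protocol".

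**The concern.** Two current texts set different contraception windows for the same women, and the looser one is the working checklist. A site can apply 5.1 and 5.2 faithfully and enrol a woman whom Table 1.0 would not admit. Because Table 1.0 is also phrased as eligibility, 13.4 would then count that enrolment as unacceptable.

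What is at stake is the sponsor's own safeguard against conception around DTG exposure. It fails to reach the criterion meant to deliver it, both at the first dose and after the last. Broken references add to this: a site looking for the permitted methods is sent to an appendix that does not exist (Table 1.0) or to the Child-Pugh table in Appendix 4 (the hormonal bullet and exclusion 28).

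**Working it through.** No sample-size or error-rate figure is involved. The check compares texts and counts days.

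**Inputs**
- Table 1.0: lead-in of 30 days; end at completion of the Follow-up visit.
- Inclusion 8: lead-in not stated for IUD, hormonal and any-other methods; tail of at least 14 days.
- Screening: "The following evaluations must be performed within 28 days prior to study randomisation" (6.4) and "BASELINE (within 28 days of screening" (Appendix 1).
- First DTG/RPV dose: baseline in the immediate-switch arm, week 48 in the deferred arm (7.1).
- Follow-up visit: 30 days after week 96, plus or minus 7 (6.9).

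**Lead-in.** Let baseline fall on day d after screening (d at most 28) and the method start on day s. Cover at first dose is d − s days, so the shortfall is 30 − (d − s).

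| Method starts (s) | Baseline (d) | Cover | Shortfall |
|---|---|---|---|
| 0 (screening day) | 28 | 28 | 2 |
| 14 | 28 | 14 | 16 |
| 28 (baseline day) | 28 | 0 | 30 |

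The range is 2 to 30 days. To meet Table 1.0 inside the window, a woman must have started 30 − d days before screening: 2 days for d = 28, 16 days for d = 14.

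**Who the lead-in gap does not reach**
- Deferred-arm women, whose first DTG/RPV dose comes 48 × 7 = 336 days after baseline.
- Women already using a method for 30 days.
- Women relying on a partner sterilised before entry.
- Women abstinent as their usual lifestyle, whom Appendix 3 exempts.

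At most it concerns women of child-bearing potential among the 100 planned for the DTG/RPV arm who start a method during or just before screening. Their number is not given.

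**Tail.** Take the last dose at the week 96 visit. Table 1.0's end point is then 30 − 7 = 23 to 30 + 7 = 37 days later. Against inclusion 8's minimum of 14 days:
- earliest: 23 − 14 = 9 days
- nominal: 30 − 14 = 16 days
- latest: 37 − 14 = 23 days

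This concerns week-96 completers in either arm who use reversible methods other than abstinence; the abstinence bullet already runs throughout the study. Early stoppers have no usable end point in Table 1.0, because 6.9 requires no Follow-up visit of them.

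**Timing.** SAP 6.1 anticipates that all participants reach week 48 by May 2021. Going back 336 days puts last entry at about June 2020. Protocol version 5.0 is dated 30 October 2020 (Appendix 6). The same SAP section places the end of week 96 visits at about June 2022, so the tail was still ahead.

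**The case against.** The best defence is that the two texts can be satisfied together. Inclusion 8's 2 weeks is a minimum, which a longer period also meets. Inclusion 4 requires willingness to comply with the protocol, and 13.4 binds sites to its restrictions, so the stricter window could be said to apply. This has some force for the tail, as does the reminder in 6.8 to avoid pregnancy while in the study. It has little for the lead-in: willingness to comply cannot supply 30 days of prior use that 5.1 never asks for.

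A second argument is that Table 1.0 could be the text to yield. It is an outline of risks, the amendment history says its pregnancy wording came from the manufacturer, and it cites an appendix this protocol lacks. The documents give no reason for 30 days. But other provisions favour the longer tail: inclusion 9 holds heterosexually active men to birth control until the follow-up visit, 6.9 schedules a home pregnancy test at that visit, and 8.3 collects pregnancy reports to 28 days after treatment.

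Third, section 6 allows 7 days either way from the Baseline visit. If that stretched baseline to day 35, a method started at screening would give 35 days of cover and no shortfall. The day counts above do not apply it, because 6.4 and Appendix 1 both state 28 days.

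A reader might infer that women may be told to stop contraception at 2 weeks, or that abstinence is 16 days short (30 − 14). Neither is supported: the 2 weeks is a floor, and the abstinence bullet is limited to a woman's usual lifestyle, which Appendix 3 exempts.

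**Conclusion.** The inconsistency stands as a minor patient-safety point. An immediate-switch woman who starts an IUD, hormonal or other low-failure method during screening can pass 5.1 and 5.2 and be dosed 2 to 30 days short of Table 1.0's lead-in. A week-96 completer may stop 9 to 23 days (nominally 16) before its end point. The figures assume baseline within 28 days of screening and the last dose at the week 96 visit.

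A reader might infer a material hazard. The documents do not support that. Table 1.0 reports neural tube defects in 0.19% with DTG exposure at conception against 0.11% without, a difference that did not reach statistical significance, and a causal link is not established. Tests at screening, before dosing at baseline and every 4 weeks reduce the risk further, though they detect pregnancy and do not prevent it. For women already on DTG (inclusion 10) a lead-in averts no new DTG exposure. Efficacy conclusions are unaffected. On the SAP's anticipated dates few or no entrants may remain, so the tail is the more relevant part; actual dates are not given.

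It is also tempting to read Appendix 3 as the right target for every reference. It presents itself as exhaustive, yet omits oral progestogen-only contraception and bilateral tubal occlusion, both allowed by exclusion 28. It covers women only, whereas exclusion 28 also covers men, and it conflicts with inclusion 8's any-other-method bullet. Nor does it contain the example listing of approved IUDs that the IUD bullet promises.

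**What to change.** In inclusion 8, require for every non-abstinence method use from at least 30 days before the first DTG/RPV dose until the Follow-up visit. For those who stop early, set a fixed period after the last dose; 30 days is suggested here to match the nominal Follow-up timing and is a reviewer's choice, not a figure from the protocol. Leave the abstinence bullet and the 28-day screening window as they are. A woman who starts a method too late is screened later or re-screened.

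Point Table 1.0's Appendix 9 reference and the hormonal bullet's Appendix 4 reference to Appendix 3. Remove exclusion 28's Appendix 4 reference and let its own list stand until it, Appendix 3 and inclusion 8's any-other-method bullet are reconciled.

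The cost is a wording amendment with no new procedure. If enrolment is still open, entry is delayed for a few women in either arm, since allocation is unknown beforehand, and some repeat screening tests. Completers on reversible methods would use contraception about 16 days longer (9 to 23) than the current minimum.

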2. OBJECTIVES AND OUTCOME MEASURES/ENDPOINTS

2.1 Primary objective

- To compare viral load outcomes on DTG/RPV FDC regimen (experimental arm) to continued ART regimen (control arm) at 48 weeks as measured by HIV-1 RNA below or confirmed above 50 copies/ML.

2.2 Secondary objectives

- To investigate whether switching patients to DTG/RPV FDC is associated with improvement of lipid profile, patient satisfaction, quality of life and potential for drug-drug interactions, investigated over time through 96 weeks with evaluation (and comparison to control arm) at week 24, 48 and 96.
- To evaluate DTG & RPV trough concentrations
- Changes in cell associated virus (using Peripheral Blood Monoclonal Cell (PBMC) analysis)

